2.6.3 Microbiome Analysis

The gut microbiome modulates immune system development,⁷¹ but the microbial populations of healthy individuals vary markedly in composition.^{72,73} The diversity of intestinal microbiota represents a careful balance between immune tolerance of beneficial microbes and inflammatory responses against pathogens. Alterations in the gut microbiota and their resulting interactions with intestinal epithelium and the host immune system are associated with many diseases, including cancer.⁷⁴ Preclinical studies have provided strong evidence for the role of gut microbiota in modulating response and resistance to immune checkpoint inhibitors, raising the possibility that stool microbiota could be used as a response biomarker for immunotherapy.^{75,76} Interestingly, postmenopausal women with breast cancer have altered composition and low diversity of their gut microbiota compared to healthy controls, as measured by the Shannon index.⁷⁷ Identification of biomarkers that predict response to immunotherapy could spare *de novo* resistant patients from the unnecessary risk of immune-related adverse events. In addition, the identification of bacterial species associated with response could open new strategies to maximize the clinical benefit of cancer immunotherapy through the modulation of gut microbiota.

Emerging evidence suggests that the gut microbiome may influence response to checkpoint inhibitors in a number of malignancies.⁷⁸⁻⁸¹ Preclinical studies in murine models have demonstrated that microbiome composition is associated with response to PD-L1 inhibitors, with mice exhibiting a “favorable” microbiome having a greater likelihood of responding to treatment as compared to mice with an “unfavorable” microbiome. Studies also demonstrate that transplanting feces from mice with favorable microbiota to those with unfavorable microbiota increases response rates, suggesting that modification of the microbiome could have a therapeutic effect in patients receiving checkpoint inhibitors.⁷⁹ Translational work demonstrates that fecal transplants from patients responding to checkpoint inhibitors to nude mice increases the likelihood of response to immunotherapy in these animals, whereas transplants from human non-responders leads to a lower likelihood of response.^{79,80} The evidence linking the gut microbiome to checkpoint inhibitor efficacy in humans has been relatively limited to date, but a number of recent publications have demonstrated a relationship between composition of the microbiome and response to immunotherapy in melanoma, non-small cell lung carcinoma and renal cell cancer.⁷⁸⁻⁸¹ Notably, the bacterial species associated with a favorable response to treatment have differed across disease sites and studies.^{78,81}

Microbiome composition is influenced by many factors, including age, genetics, and use of antibiotics and probiotics.⁸²⁻⁸⁴ Studies demonstrate that dietary composition is one of the primary drivers of microbiome diversity and taxa.^{82,83} Other factors related to energy balance, the balance of calories ingested versus expended, such as physical activity and body weight also impact microbiome composition.^{83,84} Limited data in humans suggest that factors impacting microbiome composition may also be related to checkpoint inhibitor response. An analysis of 113 patients with

metastatic melanoma found significant associations between dietary factors (ingestion of red meat [$p=0.006$], sugar-sweetened beverages [$p=0.048$] and fruits/vegetables [$p=0.049$]) and microbiome composition.⁸⁵ Use of antibiotics ($p=0.05$) and probiotics ($p=0.02$) was also associated with lower microbiome α -diversity. Exploratory analyses of 46 of these patients who were initiating treatment with anti-PD-1 therapy suggested that individuals in this cohort with a higher consumption of dietary fiber had a 5-fold likelihood of response to anti-PD-1 therapy as compared to individuals with low fiber consumption (personal communication, [name]). These findings are provocative but were based on a dietary screening tool that provides a relative crude assessment of dietary intake. The study also did not assess other modifiable factors that can influence microbiome composition, such as physical activity, precluding identification of an optimal strategy of lifestyle modification to enhance immunotherapy response.

In an effort to identify predictive biomarkers of response or resistance to immune checkpoint inhibitors, stool samples will be collected to determine whether baseline characteristics of the structure of the gut microbiome or changes in the overall diversity of gut microbiome are associated with efficacy of pembrolizumab in combination with sacituzumab govitecan in patients with HR+ / HER2- MBC. Additionally, to identify potentially modifiable drivers of microbiome diversity and composition, participants will undergo assessment of dietary composition, physical activity and body mass index at the same timepoints.

2.6.4 Pre-Screening Participants (prior to Sponsor Amendment 3, PD-L1 eligibility amendment)

The mechanisms underlying the lower response rate of HR+ MBC to immune checkpoint inhibitors are largely unknown. Lower mutation and neoantigen burden, lower levels of TILs, and lower PD-L1 expression have all been postulated as potential mechanisms but have not been systematically characterized in large numbers of patients with HR+ MBC. The archival tumor tissue required to determine the PD-L1 status of pre-screening participants presents a rich opportunity to define the immune landscape of HR+ MBC. In particular, rates of different immune cell subsets beyond TILs have been less well characterized in HR+ MBC.

Therefore, we will explore a variety of tissue biomarkers in the tumor samples from pre-screening participants, including immune cell subsets, inhibitory and costimulatory checkpoint pathway molecules, tumor mutation and neoantigen burden, and immune-related transcriptomic signatures and genomic pathway alterations. We will also define rates of PD-L1 positivity by different PD-L1 antibodies and compare rates of positivity.

3 PARTICIPANT SELECTION

Eligibility will be assessed as part of the screening procedures for all patients.

3.1 Eligibility Criteria

- 3.1.1 Participants must have histologically or cytologically confirmed invasive breast cancer with unresectable locally advanced or metastatic disease. Participants without pathologic or cytologic confirmation of metastatic disease should have unequivocal evidence of metastasis from physical examination or radiologic evaluation, i.e. visible chest wall disease or metastases on imaging meeting standard radiology criteria (i.e., lymph nodes larger than 1 cm in the short axis diameter).
- 3.1.2 Participants must have HR-positive, HER2-negative breast cancer (ER \geq 1% and/or, PR \geq 1%, HER2-negative per ASCO CAP guidelines) on local pathology review. If a patient has more than one histological result, the most recent sample will be considered for inclusion.
- 3.1.3 Participants must have either progressed on or within 12 months of adjuvant endocrine therapy within the last 12 months or have progressed on at least one line of endocrine therapy for metastatic disease and be considered appropriate candidates for chemotherapy.
- 3.1.4 Participants must have evaluable or measurable disease per RECIST 1.1. See Section 11 for the assessment of measurable disease. For instance, patients with bone only disease will be allowed to participate.
- 3.1.5 Participants must agree to undergo a research biopsy, if tumor is safely accessible, at baseline. Previously collected archival tissue will also be requested, if available, for all participants. A source of archival tumor tissue should be identified at time of registration (see Section 9 for more details). Participants must agree to a mandatory repeat biopsy 3-6 weeks after starting treatment, if tumor is safely accessible.
- 3.1.6 **Prior chemotherapy:** Participants may have received 0-1 prior chemotherapeutic regimens for metastatic breast cancer and must have been off treatment with chemotherapy for at least 14 days prior to study treatment initiation. If a prior chemotherapy was given for less than 1 cycle, it will not be counted as a prior line. No prior irinotecan or topoisomerase I-containing antibody drug conjugates in the metastatic or neo/adjuvant setting are allowed. All toxicities related to prior chemotherapy must have resolved to CTCAE v5.0 grade 1 or lower, unless otherwise specified in 3.1.15, except alopecia can be any grade and neuropathy can be grade 2 or lower.
- 3.1.7 **Prior biologic therapy:** Patients must have discontinued all biologic therapy at least 14 days prior to study treatment initiation. All toxicities related to prior biologic therapy must have resolved to CTCAE v5.0 grade 1 or lower, unless otherwise specified in 3.1.15.

- 3.1.8 **Prior targeted therapy:** Targeted therapy (e.g., prior CDK 4/6 inhibitors) must have been discontinued \geq 14 days prior to initiation of study therapy. All toxicities related to prior targeted therapy must have resolved to CTCAE v5.0 grade 1 or lower, unless otherwise specified in 3.1.15.
- 3.1.9 **Prior investigational agents for treatment of cancer:** Investigational agents must have been discontinued \geq 14 days prior to initiation of study therapy. All toxicities related to prior investigational agents must have resolved to CTCAE v5.0 grade 1 or lower, unless otherwise specified in 3.1.15.
- 3.1.10 **Prior radiation therapy:** Patients may have received prior radiation therapy. Radiation therapy must be completed at least 7 days prior to the initiation of study treatment (at least 7 days for SRS), and all toxicities related to prior radiation therapy must have resolved to CTCAE v5.0 grade 1 or lower, unless otherwise specified in 3.1.15. A 1-week washout is permitted for palliative radiation (\leq 2 weeks of radiotherapy) to non-CNS disease.
- 3.1.11 Previously treated brain metastases are permitted, with the following provisions:
- Prior SRS should complete \geq 7 days before study treatment initiation
 - Prior WBRT should complete \geq 7 days before study treatment initiation.
 - Any corticosteroid use for brain metastases must have been discontinued for \geq 7 days prior to study treatment initiation.
- 3.1.12 Participants on bisphosphonates or RANK ligand inhibitors may continue receiving therapy during study treatment and also may initiate therapy with these agents on study if clinically indicated.
- 3.1.13 The subject is \geq 18 years old.
- 3.1.14 ECOG performance status 0-1 (Karnofsky $>$ 60%, see Appendix A).
- 3.1.15 Participants must have normal organ and marrow function as defined below:
- | | |
|-----------------------------|--|
| • Absolute neutrophil count | \geq 1,000/mcL |
| • Platelets | \geq 100,000/mcL |
| • Hemoglobin | \geq 9.0 g/dL |
| • INR/PT/aPTT | \leq 1.5 \times ULN unless participant is receiving anticoagulant therapy as long as PT or aPTT is in therapeutic range of anticoagulant |
| • Total bilirubin | \leq 1.5 \times institutional upper limit of normal (ULN) (or \leq 2.0 \times ULN in patients with documented Gilbert's Syndrome) |
| • AST(SGOT)/ALT(SGPT) | \leq 2.5 \times institutional ULN or \leq 5 \times institutional ULN for participants with documented liver metastases |
| • Serum creatinine | \leq 1.5 \times institutional ULN OR creatinine |

clearance \geq 30 mL/min/ 1.73m² for participants with creatinine levels above institutional ULN.

- 3.1.16 Female subjects of childbearing potential must have a negative serum or urine pregnancy test within 2 weeks prior to study treatment initiation.

Childbearing potential is defined as participants who have not reached a postmenopausal state (\geq 12 continuous months of amenorrhea with no identified cause other than menopause) and have not undergone surgical sterilization (removal of ovaries and/or uterus).

- 3.1.17 Women of childbearing potential (WOCBP) must agree to use an adequate method of contraception. Contraception is required starting with the first dose of study medication through 180 days (6 months) after the last dose of study medication. Examples of contraceptive methods with a failure rate of $< 1\%$ per year include bilateral tubal ligation, male sterilization, and copper intrauterine devices. Periodic abstinence (e.g., calendar, ovulation, symptothermal, or post-ovulation methods) and withdrawal are not acceptable methods of contraception. Hormonal contraceptives are contraindicated for HR+ breast cancer (Appendix B).
- 3.1.18 Males who are sexually active with WOCBP must agree to follow instructions for method(s) of contraception for the duration of study treatment with pembrolizumab and 3 months after the last dose of study treatment (Appendix B).
- 3.1.19 The participant must be capable of understanding and complying with the protocol and willing to sign a written informed consent document.

3.2 Exclusion Criteria

- 3.2.1 Prior therapy with any anti-PD-1, PD-L1, or PD-L2 agent or sacituzumab govitecan (IMMU-132). Prior therapy with irinotecan or topoisomerase I-containing antibody drug conjugates at any time for early stage or metastatic disease.
- 3.2.2 Prior hypersensitivity to the excipients of pembrolizumab or sacituzumab govitecan (IMMU-132) therapy.
- 3.2.3 Known history of UDP-glucuronosyltransferase 1A1 (UGT1A1) *28 allele homozygosity, which is associated with increased risk for neutropenia and diarrhea related to irinotecan.⁸⁶

Note: Concurrent administration of strong UGT1A1 inhibitors or inducers is not allowed during the course of the study (See Section 5.6.2).

- 3.2.4 Known brain metastases that are untreated, symptomatic, or require therapy to control symptoms.

- 3.2.5 Participant has known leptomeningeal disease.
- 3.2.6 Major surgery within 2 weeks prior to study treatment initiation. Patients must have recovered from any effects of any major surgery.
- 3.2.7 Uncontrolled, significant intercurrent or recent illness including, but not limited to, ongoing or active infection, uncontrolled non-malignant systemic disease, uncontrolled seizures, or psychiatric illness/social situation that would limit compliance with study requirements in the opinion of the treating investigator.
- 3.2.8 Participant has a medical condition that requires chronic systemic steroid therapy (> 10 mg of prednisone daily or equivalent) or any other form of immunosuppressive medication (including disease modifying agents) and has required such therapy in the last 2 years. Replacement therapy (e.g. thyroxine, insulin, or physiologic corticosteroid replacement therapy for adrenal or pituitary insufficiency, etc.) is not considered a form of systemic therapy.
- 3.2.9 Participant has documented history of autoimmune disease or syndrome that currently requires systemic steroids or immunosuppressive agents.
- 3.2.10 History of (non-infectious) pneumonitis/interstitial lung disease that required steroids or current pneumonitis/interstitial lung disease.
- 3.2.11 Individuals with a history of a second malignancy are ineligible except for the following circumstances. Individuals with a history of other malignancies are eligible if they have been disease-free for at least 3 years or are deemed by the investigator to be at low risk for recurrence of that malignancy. Individuals with the following cancers that have been diagnosed and treated within the past 3 years are eligible: cervical/prostate carcinoma *in situ*, superficial bladder cancer, non-melanoma cancer of the skin. Patients with other cancers diagnosed within the past 3 years and felt to be at low risk of recurrence should be discussed with the study principal investigator to determine eligibility.
- 3.2.12 Participant has a known history of human immunodeficiency virus (HIV), Hepatitis B (defined as Hepatitis B surface antigen [HBsAg] reactive) or known active Hepatitis C virus (defined as detected HCV RNA [qualitative]) infection. HIV-positive participants are ineligible due to the potential for pharmacokinetic interactions of combination antiretroviral therapy with study drugs and the increased risk of fatal infections. Note: No testing for HIV, Hepatitis B, or Hepatitis C is required unless mandated by local health authority.

- 3.2.13 The participant has received a live vaccine within 28 days prior to study treatment initiation. Examples of live vaccines include, but are not limited to, the following: measles, mumps, rubella, varicella/zoster, yellow fever, rabies, BCG, and typhoid vaccine. The use of the inactivated seasonal influenza vaccine is allowed.
- 3.2.14 Has a history or current evidence of any condition, therapy, or laboratory abnormality that might confound the results of the study, interfere with the subject's participation for the full duration of the study, or is not in the best interest of the subject to participate, in the opinion of the treating investigator.
- 3.2.15 It is unknown whether pembrolizumab is excreted in human milk. Since many drugs are excreted in human milk, and because of the potential for serious adverse reactions in the nursing infant, participants who are breast-feeding are not eligible for enrollment.

3.3 Retreatment Eligibility Criteria

In addition to the above criteria aside from prior treatment with sacituzumab govitecan and pembrolizumab, the following eligibility criteria are required:

- 3.3.1 The participant stopped initial treatment with sacituzumab govitecan and/or pembrolizumab after attaining an investigator-assessed CR according to RECIST 1.1, confirmed in at least two consecutive restaging scans, was treated for at least 24 weeks with pembrolizumab and/or sacituzumab govitecan before discontinuing therapy, and received at least three cycles (with pembrolizumab and sacituzumab govitecan (Arm A) or sacituzumab govitecan alone (Arm B)) beyond the date when the initial CR was declared.
- 3.3.2 The participant experienced an investigator-assessed or radiographic disease progression after stopping their initial treatment with sacituzumab govitecan and/or pembrolizumab (Arm A) or sacituzumab govitecan (Arm B).
- 3.3.3 The participant did not receive any anti-cancer treatment other than sacituzumab govitecan (or pembrolizumab) since the last dose of pembrolizumab (or sacituzumab govitecan) for Arm A; the participant did not receive any anti-cancer treatment since the last dose of sacituzumab govitecan for Arm B.
- 3.3.4 Participants must agree to undergo a research biopsy, if tumor is safely accessible, prior to retreatment. Participants must agree to a mandatory repeat biopsy at the time of disease progression on retreatment, if a complete or partial response, or stable response for ≥ 6 months was achieved during the retreatment phase.
- 3.3.5 Prior radiation therapy: Patients may have received prior radiation therapy. Radiation therapy must be completed at least 7 days prior to retreatment initiation (at least 7 days for SRS), and all toxicities related to prior radiation therapy must have resolved to CTCAE v5.0 grade 1 or lower, unless otherwise specified in 3.3.8.

- 3.3.6 Stable, previously treated brain metastases are permitted, with the following provisions:
- Prior SRS should complete \geq 7 days before study treatment initiation
 - Prior WBRT should complete \geq 7 days before study treatment initiation
 - Any corticosteroid use for brain metastases must have been discontinued for \geq 7 days prior to retreatment initiation.
- 3.3.7 ECOG performance status 0-1 (Karnofsky $>60\%$, see Appendix A).
- 3.3.8 Participants must have normal organ and marrow function as defined below:
- | | |
|-----------------------------|---|
| • Absolute neutrophil count | $\geq 1,000/\text{mcL}$ |
| • Platelets | $\geq 100,000/\text{mcL}$ |
| • Hemoglobin | $\geq 9.0 \text{ g/dL}$ |
| • INR/PT/aPTT | $\leq 1.5 \times \text{ULN}$ unless participant is receiving anticoagulant therapy as long as PT or aPTT is in therapeutic range of anticoagulant |
| • Total bilirubin | $\leq 1.5 \times$ institutional upper limit of normal (ULN)
(or $\leq 2.0 \times \text{ULN}$ in patients with documented Gilbert's Syndrome) |
| • AST(SGOT)/ALT(SGPT) | $\leq 2.5 \times$ institutional ULN or
$\leq 5 \times$ institutional ULN for participants with documented liver metastases |
| • Serum creatinine | $\leq 1.5 \times$ institutional ULN OR creatinine clearance $\geq 30 \text{ mL/min/} 1.73\text{m}^2$ for participants with creatinine levels above institutional ULN. |
- 3.3.9 Female subjects of childbearing potential must have a negative serum or urine pregnancy test within 2 weeks prior to study treatment initiation.
- Childbearing potential is defined as: participants who have not reached a postmenopausal state (≥ 12 continuous months of amenorrhea with no identified cause other than menopause) and have not undergone surgical sterilization (removal of ovaries and/or uterus).
- 3.3.10 Women of childbearing potential (WOCBP) must agree to use an adequate method of contraception. Contraception is required starting with the first dose of study medication through 180 days (6 months) after the last dose of study medication. Examples of contraceptive methods with a failure rate of $< 1\%$ per year include bilateral tubal ligation, male sterilization, established and proper use of hormonal contraceptives that inhibit ovulation, hormone-releasing intrauterine devices, and copper intrauterine devices. Periodic abstinence (e.g., calendar, ovulation, symptothermal, or post-ovulation methods) and withdrawal are not acceptable methods of contraception (Appendix B).

- 3.3.11 Males who are sexually active with WOCBP must agree to follow instructions for method(s) of contraception for the duration of study treatment with pembrolizumab and 3 months after the last dose of study treatment (Appendix B).
- 3.3.12 Participants on bisphosphonates or RANK ligand inhibitors may continue receiving therapy during study treatment and also may initiate therapy with these agents on study if clinically indicated.

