In the event of unusual or life-threatening complications, treating investigators must immediately notify the Sponsor-Investigator, [name], [contact], or email: [contact] .

Second Course Phase Therapy:

Retreatment Phase (available to both Arms)

Participants who stop sacituzumab govitecan and/or pembrolizumab with CR after at least 24 weeks of treatment may be eligible for additional pembrolizumab and/or sacituzumab govitecan therapy if they progress after stopping study treatment. For participants randomized to the combination arm (Arm A): if both sacituzumab govitecan and pembrolizumab are discontinued and participant experiences progression, both sacituzumab govitecan and pembrolizumab can be restarted at physician's discretion; or if sacituzumab govitecan is discontinued and pembrolizumab is continued and participant experiences progression, sacituzumab govitecan can be added to the pembrolizumab at physician's discretion. For participants randomized to sacituzumab govitecan monotherapy (Arm B): if sacituzumab govitecan is discontinued and participant experiences progression, sacituzumab govitecan can be restarted at physician's discretion. This retreatment is termed the Second Course Phase of this study and is only available if the study remains open and the subject meets the following conditions:

- Stopped initial treatment with sacituzumab govitecan and/or pembrolizumab after attaining an investigator-assessed CR according to RECIST 1.1, confirmed in at least two consecutive restaging scans, was treated for at least 24 weeks with pembrolizumab and/or sacituzumab govitecan before discontinuing therapy, and received at least three cycles (with pembrolizumab and sacituzumab govitecan (Arm A) or sacituzumab govitecan alone (Arm B)) beyond the date when the initial CR was declared

AND

- Experienced an investigator-assessed or radiographic disease progression after stopping their initial treatment with sacituzumab govitecan and/or pembrolizumab (Arm A) or sacituzumab govitecan (Arm B)
- Did not receive any anti-cancer treatment other than:
 - Arm A: Sacituzumab govitecan (or pembrolizumab) since the last dose of pembrolizumab (or sacituzumab govitecan)
 - Arm B: No other anti-cancer treatment since the last dose of sacituzumab govitecan

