- Participants who stop pembrolizumab after receiving 35 doses may be eligible for retreatment if they progress after stopping study treatment, provided they meet the requirements detailed in Sections 3.3 and 3.4. Participants may be retreated in the Second Course Phase (Retreatment) for up to an additional 17 cycles (approximately 1 year).

The retreatment section of the eligibility checklist should be completed and signed by the treating investigator. DF/HCC sites will re-send the checklist to ODQ for processing. Non-DF/HCC sites will email documentation to the Coordinating Center at [contact] for review. Provided the patient meets criteria per protocol for retreatment, the Coordinating Center will process the checklist and the participating site will be notified that the patient may proceed to retreatment.

Subjects who restart treatment will be retreated at the same dose and dose interval as when they last received pembrolizumab and/or sacituzumab govitecan. Visit requirements are as outlined for subjects on the initial treatment phase of the trial. These participants may resume the scan schedule they had previously during the treatment break, i.e., every 9 weeks.

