Female participants of childbearing potential are eligible to participate if they agree to use a highly effective method of contraception consistently and correctly as described in Table 1 starting with the first dose of study medication through 180 days (6 months) after the last dose of study medication.

Table 1 Highly Effective Contraception Methods

Highly Effective Methods That Have Low User Dependency Failure rate of <1% per year when used consistently and correctly.

• Intrauterine device (IUD)• Bilateral tubal occlusion

• Vasectomized partner A vasectomized partner is a highly effective contraception method provided that the partner is the sole male sexual partner of the WOCBP and the absence of sperm has been confirmed. If not, an additional highly effective method of contraception should be used.

• Sexual abstinence Sexual abstinence is considered a highly effective method only if defined as refraining from heterosexual intercourse during the entire period of risk associated with the study treatment. The reliability of sexual abstinence needs to be evaluated in relation to the duration of the study and the preferred and usual lifestyle of the participant.)

Notes: Use should be consistent with local regulations regarding the use of contraceptive methods for participants of clinical studies.

Pregnancy Testing

WOCBP should only be included after a negative highly sensitive urine or serum pregnancy test.

Following initiation of treatment, pregnancy testing will be performed whenever an expected menstrual cycle is missed or when pregnancy is otherwise suspected; at the time points specified in the Schedule of Activities, and as required locally.

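### Retreatment criterion 3.3.10 offers hormonal contraceptives and hormone-releasing IUDs as examples, although 3.1.17, still in force at retreatment, calls hormonal contraceptives contraindicated in HR+ breast cancer

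*Combined protocol and SAP*

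**What the plan says.** Section 3.1.17 (first entry) requires contraception up to 180 days after the last dose. As examples with a failure rate under 1% per year it gives "bilateral tubal ligation, male sterilization, and copper intrauterine devices", and it adds "Hormonal contraceptives are contraindicated for HR+ breast cancer (Appendix B".

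Section 3.3.10 (retreatment) sets the same duration and failure-rate threshold and gives the same three methods, but also "established and proper use of hormonal contraceptives that inhibit ovulation, hormone-releasing intrauterine devices". It does not carry the contraindication sentence.

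Section 3.3 opens with "In addition to the above criteria aside from prior treatment with sacituzumab govitecan and pembrolizumab", so the retreatment criteria add to the first-entry criteria and waive only the one on prior study treatment.

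Both criteria refer to Appendix B. There, female participants of childbearing potential must "agree to use a highly effective method of contraception consistently and correctly as described in Table 1". That table lists four methods: intrauterine device (type not stated), bilateral tubal occlusion, vasectomized partner and sexual abstinence.

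**The concern.** Section 3.1.2 restricts the trial to HR+ disease, so the contraindication in 3.1.17 covers every woman of childbearing potential enrolled. A retreatment criterion that offers two hormonal methods as examples contradicts it. A site working from 3.3.10 alone could accept a method that the same protocol calls contraindicated. Section 5.7 makes this plausible: the treating investigator signs a separate retreatment section of the eligibility checklist, and patients who stop after 35 pembrolizumab doses may be retreated "provided they meet the requirements detailed in Sections 3.3 and 3.4", which sends the reader to the sections without the warning. At stake is the safety of individual participants. No endpoint, efficacy analysis, power or type I error is involved.

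**Working it through.** The plan gives no figure to reproduce. The check compares texts, followed by a rough bound on reach.

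**1. Methods listed**

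| Place | Methods named | Hormonal | Contraindication stated? |
|---|---|---|---|
| 3.1.17 | 3: tubal ligation, male sterilization, copper IUD | 0 | Yes |
| 3.3.10 | 5: the same three, ovulation-inhibiting hormonal contraceptives, hormone-releasing IUD | 2 | No |
| Appendix B Table 1 | 4: IUD, tubal occlusion, vasectomized partner, abstinence | 0 named; IUD type open | No |

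The lists in 3.1.17 and 3.3.10 differ by exactly the two hormonal items (5 − 2 = 3). No reason for a different rule at retreatment is given. A correction made to 3.1.17 and not carried across would explain it, but that is an inference.

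**2. Do both criteria apply together?** Yes. The Section 3.3 lead-in lifts only the prior-treatment criterion, so 3.1.17 still binds.

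**3. Does Appendix B resolve it?** In part. Table 1 governs female participants and names no hormonal contraceptive, so ovulation-inhibiting methods are out. The IUD entry excludes no type. Appendix B asks for non-hormonal methods only from women on hormone replacement whose menopausal status is in doubt, which does not cover other women of childbearing potential. For the hormone-releasing IUD, therefore, 3.3.10 names it, Table 1 does not exclude it, and 3.1.17 excludes it only by natural reading, because the only IUD it lists is copper.

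**4. How many could be affected?** Section 3.3.1 requires that "The participant stopped initial treatment with sacituzumab govitecan and/or pembrolizumab after attaining an investigator-assessed CR according to RECIST 1.1", confirmed on at least two consecutive restaging scans. The 35-dose route also passes through Section 3.3, so it is not added as a further group. The only complete-response count that the protocol gives for sacituzumab govitecan in breast cancer is 3 of 108, in triple-negative disease (Section 2.4.5).

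- Rate: 3/108 = 2.78%; Clopper-Pearson 95% interval 0.58% to 7.90%.
- Applied to the planned 110 patients, as an assumption: 110 × 0.0278 = 3.1; limits 110 × 0.00577 = 0.6 and 110 × 0.0790 = 8.7.

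These are patients who might meet the complete-response condition, before progression after stopping and the other conditions of 3.3 and 3.4. The documents do not give the share of women of childbearing potential, so no number of women is estimated.

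**5. Could a woman reach retreatment on a hormonal method?** She agreed to 3.1.17 at first entry, so this would normally need a later change of method. The 3.1.17 obligation ends 180 days after the last dose, and progression after stopping can come later than that, so a change between courses is possible.

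**The case against.** The best defence is that the protocol already contains the answer. Sections 3.1 and 3.3 must both be met, and 3.3.10 itself points to Appendix B, so a site that follows the text excludes ovulation-inhibiting contraceptives. Section 3.3.10 gives examples of methods with a low failure rate; it does not instruct anyone to use them. The Office of Data Quality or the Coordinating Center also handles the retreatment checklist before a patient proceeds. All of this stands and is why the point is minor. It does not make 3.3.10 correct: a criterion should not offer as an example a method that another binding criterion calls contraindicated.

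It is also fair to say that nothing states outright that a hormone-releasing IUD is contraindicated, and that the copper IUD in 3.1.17 is itself only an example. That limit stands. The mismatch between 3.1.17 and 3.3.10 is certain; the IUD part rests on a natural reading.

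Finally, the complete-response range is borrowed from later-line triple-negative patients on monotherapy, whereas this trial enrols HR+ patients with at most one prior chemotherapy line for metastatic disease and gives half of them a combination. It is no more than an illustration that the group is small.

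**Conclusion.** The concern holds as a minor participant-safety inconsistency. Two of the five example methods in 3.3.10 conflict with 3.1.17 in a trial population that is entirely HR+. Appendix B removes the conflict for ovulation-inhibiting contraceptives but not clearly for hormone-releasing IUDs. Reach is small and may be zero: Section 13.2.1 reports accrual complete, and retreatment "is only available if the study remains open and the subject meets the following conditions". The 0.6 to 8.7 range depends on carrying a triple-negative complete-response rate over to this population and counts patients before the remaining conditions, including childbearing potential. The conclusion about the text does not depend on that range.

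**What to change.** - **Section 3.3.10:** delete "established and proper use of hormonal contraceptives that inhibit ovulation, hormone-releasing intrauterine devices", leaving the same three methods as 3.1.17, and repeat the 3.1.17 sentence on the contraindication.
- **Appendix B Table 1:** add a note that for female participants the IUD must be copper (non-hormonal), and that this limit does not apply to female partners of male participants, who are not the patients with HR+ disease.
- **Side correction in the same edit:** the male-participant paragraph of Appendix B sends partners to a Table 9 that does not appear in the appendix text. Correct that reference, probably to Table 1, so that the partner exemption attaches to the table actually cited.

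The cost is amendment wording only. Requirements for partners, data collection, analysis and sample size do not change.
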